## 6 Study Endpoints

### 6.1 Primary Endpoints

- Cumulative incidence of SADR, including malignancies and serious infections
- Time to resolution of lymphopenia, among registry participants with persistent lymphopenia

- Cumulative incidence of all AEs in the “Blood and Lymphatic System Disorders” System Organ Class (SOC) and in the “Neoplasms Benign, Malignant, and Unspecified” SOC

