### **Safety Analysis**

#### ***Primary Endpoints***

*The cumulative incidence of SADRs and of AEs in the ‘Blood and Lymphatic System Disorders’ and ‘Neoplasms Benign, Malignant, and Unspecified’ SOCs will be summarized, and time to resolution of persistent lymphopenia will be estimated using the life table methodology. The first occurrence of each endpoint occurring during the cumulative analysis period will be considered in the analysis. Cumulative incidence analyses will be presented by MedDRA System Organ Class, High Level Group Term, High Level Term, and Preferred Term.*

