TLF	Tables, Listings, and Figures
WHO-DD	World Health Organization Drug Dictionary

3 Modification History

Unique Identifier for Version	Date of IAP Version	Author	Changes from the Previous Version
NA			

4 Purpose of the Integrated Analysis Plan

The purpose of this IAP (integrated analysis plan) is to document technical and detailed statistical specifications for the final analysis of data collected for protocol EMR700568-012 called PREMIERE. Results of the analyses described in this IAP will be included in the Clinical Study Report (CSR). Additionally, the planned analyses identified in this IAP will be included in regulatory submissions or future manuscripts. Any post-hoc, or unplanned analyses performed to provide results for inclusion in the CSR but not identified in this prospective IAP will be clearly identified in the CSR.

The IAP is based upon section 9 (Data Analysis and Statistics) of the study protocol and protocol amendments and is prepared in compliance with International Conference on Harmonization (ICH) E9 and Guidelines for Good Pharmacoepidemiology Practices (GPP). It describes analyses planned in the protocol and protocol amendments.

5 Objectives and Endpoints

Objectives	Endpoints (Outcome Measures)	Endpoints (Outcome Measures) Timeframe	IAP section
Primary			

 To quantify and characterize the risk (cumulative incidence) of serious adverse drug reaction (SADR), including malignancies and serious infections To assess time to resolution of lymphopenia among registry participants with persistent lymphopenia To quantify and characterize the risk (cumulative incidence) of AE in the 'Blood and Lymphatic System Disorders' and 'Neoplasms Benign, Malignant, and Unspecified' System Organ Classes (SOCs) 	
 Cumulative incidence of SADR, including malignancies and serious infections Time to resolution of lymphopenia, among registry participants with persistent lymphopenia Cumulative incidence of all AEs in the "Blood and Lymphatic System Disorders" System Organ Class (SOC) and in the "Neoplasms Benign, Malignant, and Unspecified" SOC 	
 AE crude incidence from Registry Day 1 to End of registry Time to resolution of lymphopenia, for participants with ongoing lymphopenia at the end of clinical trial AE crude incidence from Registry Day 1 to End of registry 	
 Section 15.1.1 Section 15.1.4 Section 15.1.2 & 15.1.3

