Section 9.2.2 Treatment/Analysis periods	Demographic characteristics (e.g., age, sex) at baseline of the registry will be described using descriptive statistics for continuous variables or proportions for categorical variables at entry into the registry. Summaries will be provided by region/country.	Demographic characteristics will not be summarized by region/country. Instead, based on the understanding of the protocol, summary statistics for the number of subjects by country will be provided.
Section 9.2.1 General Considerations	Time to resolution of persistent lymphopenia will be estimated using the life table methodology.	
The time to resolution of lymphopenia (duration of lymphopenia episode) has already been presented in the ISS using the product-limit method of Kaplan and Meier. This analysis will not be repeated.
 
The time to resolution of lymphopenia for participants with ongoing lymphopenia at end of clinical trial will be analyzed using descriptive statistics.

Section 9.2.1 General Considerations	The main analysis will be to estimate cumulative incidence rates using life-table methodology.	
The main analysis of adverse events will be done on the period from the end of clinical trial + 1 day to the last date in PREMIERE registry. The life-table methodology will not be used. Rather, the crude incidence will be presented with the corresponding 95% confidence interval.
 
The time to first event from the first dose of cladribine has already been presented in the ISS following the Kaplan-Meier methodology for AESI infections and malignancies. Therefore, it will not be repeated here.

Section 10.2 Subject information and informed consent	Subjects who refuse to enroll in the registry will be asked to sign consent (see CRF: Data Release Participant only) for use of their clinical trial data to compare registry non-participants with registry participants in terms of demographics, cancer risk factors and severity of MS.	Comparison of registry participant's vs non-registry participants will not be performed due to very strong sample size imbalance between the 2 groups. Indeed as the registry target population was of 2175 subjects, 1161 patients enrolled as full participants and 22 refused and signed the data release consent form only.
---	---	---

8 Protocol Deviations and Analysis Populations

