Data collected from last value from the end of clinical trial to the last ALC value in PREMIERE will be presented and summarized on a continuous manner (absolute value only) and by grade, over time.

ALC Registry Baseline is defined as the first ALC date with a value on or after the end of clinical trial +1 day [Registry Day 1].

Programming rule to cover possible unclean data:

If first ALC date in PREMIERE is before the end of clinical trial, ALC Registry Baseline is defined as the first ALC value in PREMIERE on or after the end of clinical trial + 1 day.

A new set of time window are presented below using visit window computed relative to ALC Registry Baseline.

If more than 1 value is available for a particular time window for the same subject, the first value in the time window will be considered.

Table 8 Time window for lymphocyte from the end of clinical trial

Evaluation	Interval for analysis (day)
Last value from last clinical trial	
ALC Registry Baseline	First ALC date with value in PREMIERE registry
Week 12	[2 - 98]
Week 24	[99 - 182]
Week 36	[183 - 266]
Week 48, 1y	[267 - 350]
Week 60	[351 - 434]
Week 72	[435 - 518]
Week 84	[519 - 602]
Week 96, y2	[603 - 700]
Week 144, y3	[701 - 1036]
Etc.	[1037 - weekN*7+4*7]

Lymphopenia grade and MS-DMD

Best and Worst ALC grades will be presented in relation to use of MS-DMD medication. For subjects with MS-DMD medications reported at least once after end of clinical trial, the best and worst ALC grade will be selected on or after (\geq) the first MS-DMD.

The Worst and the Best grade will be summarized overall and by treatment group. Subjects who are not taking MS-DMD from the end of clinical trial +1 day to the end of PREMIERE will be excluded from the analysis.

Resolution of lymphopenia computed with observed ALC value

Subjects who complete or drop out at the end of the clinical trial with an unresolved lymphopenia will be presented, together with their outcome in PREMIERE registry. The outcome can be resolved or unresolved.

An unresolved lymphopenia is defined for a subject who left the end of a clinical trial without returning to normal or grade 1 ALC value after an episode of grade 3 or 4 lymphopenia. A grade 3 or 4 lymphopenia episode is defined by a start/end date. Start= ALC \geq grade 3, post baseline, End = following normal (grade 0) or grade 1.

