The duration (in months) of the resolved episodes (out of the unresolved at end of clinical trial period) will be summarized. In addition, use of MS-DMDs prior to resolution will be presented.

Resolution of lymphopenia computed using CRF tick box

Reporting will be done for SAF. This is an exception, to include the largest possible information available.

The number of subjects with declared Grade 3 or 4 lymphopenia at end of clinical trial [CRF Tick box], will be summarized together with their outcome in PREMIERE. The outcome in PREMIERE will be computed from those with at least one grade 0/1 in PREMIERE or with a CRF "resolution date".

Presentation per treatment group and total will be done.

Resolution of lymphopenia based on observed ALC value versus CRF tick box

A 2-by-2 table of number of subjects with and without resolution of lymphopenia at the end of clinical trial based on ALC value versus CRF Tick box will be presented.

In addition, a listing will be generated for subjects with unresolved lymphopenia at the end of clinical trial according to ALC grade, but with the CRF Tick box = "Resolved". The following variables will be displayed: Subject ID, cumulative dose of cladribine, previous clinical trial, treatment group (see section 9.1), all ALC values in PREMIERE with grade and date and tick box for resolved with date of resolved if available.

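### The SAP's only time-to-resolution summary for persistent lymphopenia covers resolved episodes; unresolved subjects add no follow-up time to a primary endpoint

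*SAP*

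**What the plan says.** Protocol 6.1 lists as a primary endpoint "Time to resolution of lymphopenia, among registry participants with persistent lymphopenia". Protocol 6.3 counts a subject as persistent if he or she leaves the trial at Grade 3 or 4, and as resolved on reaching Grade 1 or 0. The analysis text under Protocol 9.2.2 plans that "time to resolution of persistent lymphopenia will be estimated using the life table methodology". Protocol 9.3.1 adds that subjects who stop responding are censored in time-to-event analyses and leaves the details to the SAP.

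SAP Section 5 keeps the endpoint: "Time to resolution of lymphopenia, for participants with ongoing lymphopenia at the end of clinical trial". SAP Section 7, Table 1, declares a change of method. It says that time to resolution, described there as episode duration, "has already been presented in the ISS using the product-limit method of Kaplan and Meier. This analysis will not be repeated". It then says: "The time to resolution of lymphopenia for participants with ongoing lymphopenia at end of clinical trial will be analyzed using descriptive statistics".

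SAP 15.1.4 presents the subjects who left the trial unresolved, with their registry outcome: "The outcome can be resolved or unresolved". The time summary follows: "The duration (in months) of the resolved episodes (out of the unresolved at end of clinical trial period) will be summarized". On the clock, the SAP says: "A grade 3 or 4 lymphopenia episode is defined by a start/end date". The start is a post-baseline count of Grade 3 or worse, and the end is the next Grade 0 or 1. The same section tabulates absolute lymphocyte count (ALC) by grade across registry windows and gives counts by outcome from a CRF tick box.

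**The concern.** A time to resolution has to use the time of everyone at risk of resolving, including those who never do. The protocol expects such subjects: Section 5.7 arranges further follow-up for lymphopenia still open when the registry closes. Follow-up can also stop at the 8-year limit, at withdrawal, at loss to follow-up, or on entry into an interventional study. If only resolved episodes supply durations, the summary answers a different question: how long the episodes lasted among those that ended within observation. The counts beside it show how many did not resolve, but give no time for them.

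This is a primary endpoint of a long-term safety registry. A reader of the study report could take the median of resolved episodes for the time a lymphopenic patient should expect to wait.

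**Working it through.** The documents give no number of persistent cases, no share resolved and no expected median, so there is no plan figure to reproduce. The check has five parts.

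**1. Who contributes what under SAP 15.1.4**

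| Output | Resolved subjects | Unresolved subjects |
|---|---|---|
| Outcome counts | counted | counted |
| ALC by grade over time (whole lymphocyte population) | included | included while they have counts |
| Duration in months | included | no contribution |

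SAP 15.1.4 gives no censoring rule. SAP 9.14 bases interpretation on point estimates with 95% confidence intervals, but the statistics listed for continuous variables in SAP 9.13 include no interval.

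**2. Bound on the same subjects and clock, no delayed entry**

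Let n subjects be followed, d resolve, and p = d/n. The Kaplan-Meier weight on each resolution is at least 1/n, does not decrease over time, and all weights sum to at most 1. So at the k-th resolution

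k/n ≤ F_KM ≤ k/d.

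The right side means that F_KM cannot pass 0.5 before k = d/2, the 50th percentile of resolved durations. The left side means that it must reach 0.5 by k = n/2, which is the (50/p)th percentile of resolved durations.

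| Share resolved p | Upper end, 50/p |
|---|---|
| 95% | 52.6th percentile |
| 90% | 55.6th |
| 80% | 62.5th |
| 67% | 75th |
| 50% | longest resolved duration |

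Below 50% resolved, the Kaplan-Meier median may not be reached.

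**3. Illustration under assumed values**

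Assume exponential resolution times and censoring uniform over 12 to 72 months, with 200,000 simulated subjects per row. None of these inputs comes from the documents.

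| True median (months) | Resolved | Resolved-only median | Kaplan-Meier median |
|---|---|---|---|
| 6 | 96.4% | 5.7 | 6.0 |
| 12 | 86.1% | 9.7 | 12.0 |
| 24 | 66.5% | 14.0 | 23.9 |
| 36 | 53.0% | 16.1 | 35.9 |
| 60 | 37.2% | 18.1 | 60.2 |

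**4. What the ISS could have seen**

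Inputs: ISS long-term cut-off 15 May 2017 (SAP Section 7, Table 1); last visit 25 October 2018 (SAP Section 6); follow-up limit 8 years from first trial enrolment (Protocol 5.7).

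Gap = min(first enrolment + 8 years, 25 October 2018) − 15 May 2017, with 30.4375 days per month (365.25/12, SAP 9.11).

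- Enrolled on or before 15 May 2009: 0 days.
- 15 November 2009: 184 days, 6.0 months.
- 15 May 2010: 365 days, 12.0 months.
- 25 October 2010 or later: 528 days, 17.3 months.

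Protocol 5.7 implies that the last inclusion was in 2010.

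**5. Who is in the set**

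Protocol 6.3 requires Grade 3 or 4 when the subject leaves the trial. SAP 15.1.4 requires only that the count has not returned to Grade 0 or 1 after a Grade 3 or 4 episode. A subject who had recovered to Grade 2 by trial end is in the SAP set and outside the protocol's. Table 1 does not mention this.

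**The case against.** The strongest reply is that the change is declared and reasoned. Table 1 names the dropped method, says where the Kaplan-Meier analysis can be found and states the replacement. It also describes the ISS long-term data as covering all subjects, enrolled in the registry or not, so registry participants are among them. That stands, and it rules out calling this a hidden departure. It does not settle the matter. Table 1 itself separates episode duration, which is in the ISS, from time to resolution in participants still lymphopenic at trial end, which is given to descriptive statistics. The second is the registry's endpoint.

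A reader might infer that no censored estimate exists anywhere for these participants. The documents do not support that, because the ISS is not among them; all that can be said is that coverage of this subset is not shown. The 17.3 months is likewise a per-subject ceiling. The cut-off of the ISS lymphopenia analysis itself is not stated, nor is the number of lymphopenic subjects followed beyond 15 May 2017.

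A reader might also infer that unresolved subjects vanish from the report. They do not: they appear in the outcome counts and, while they have values, in the ALC tables.

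The bound in part 2 is open to a fair criticism. The SAP set is selected as still open at trial end while the clock starts in the trial, which is delayed entry. The bound therefore concerns a simple same-clock estimate, not the one recommended below.

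The broader SAP set has some footing, since Protocol 5.7 describes ongoing lymphopenia as not having reached Grade 0 or 1. It is still not the Protocol 6.3 definition. A reader might go further and say that the 2-by-2 table against the tick box compares two definitions. That cannot be asserted: SAP 15.1.4 describes the tick box both as declared Grade 3 or 4 at trial end and as a box marked resolved, so it is unclear which is used.

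**Conclusion.** The concern holds as a structural point. Within this SAP, the only time summary for primary endpoint 2 conditions on resolving, uses no follow-up from unresolved subjects and has no confidence interval. It can be read as time to resolution only if nearly all subjects resolve.

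The size cannot be computed from the documents. On the same subjects and clock, the resolved-only median is never longer than the Kaplan-Meier median. The two are close at 95% resolved and may be far apart once a third or more stay unresolved. It would be wrong to conclude that the SAP figure must understate the time to resolution. Leaving out unresolved subjects shortens it. Starting the clock in the trial for episodes selected as still open at trial end lengthens it, and detection can lag because Protocol 8.4 asks for counts only at least yearly. Against an estimate timed from trial end, the net direction is not fixed.

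No hypothesis test is affected, since none is planned. The point is worth correcting because the endpoint is primary and the remedy is small.

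**What to change.** 1. Add one Kaplan-Meier or life-table estimate of time from end of clinical trial (SAP 9.8) to first Grade 0 or 1 ALC, in subjects meeting Protocol 6.3, that is, Grade 3 or 4 at trial end. Using trial end as origin avoids delayed entry.
2. Censor unresolved subjects at their last ALC with a value (SAP 9.10). State how many eligible subjects have no post-trial ALC, since they fall outside the Lymphocyte Analysis Population and add no time.
3. Report the median with 95% confidence interval, numbers at risk and percent resolved.
4. Label the existing duration summary as applying to resolved episodes only.
5. Add a Table 1 entry saying that the SAP's unresolved set admits subjects at Grade 2 at trial end, unlike Protocol 6.3, and keep that set as a sensitivity analysis.

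An interval-censored analysis for sparse counts is optional. Leave the 2-by-2 table alone unless the sponsor confirms which tick box it uses.

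The cost is SAP wording, one Table 1 row, one population flag and one survival procedure, repeated for the sensitivity set, on dates the SAP already derives. The reported time may lengthen or shorten: censored follow-up lengthens it, and moving the origin to trial end shortens it.

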## 6.3 Definitions related to study Endpoints

### Resolution of Persistent Lymphopenia

Subjects who complete or drop out of a cladribine clinical trial with a Grade 3 or Grade 4 lymphopenia as defined by the Common Terminology Criteria for Adverse Events (CTCAE) [8] will be defined as having ‘persistent lymphopenia’ and will be monitored until lymphopenia resolves. Resolution is the achievement of a CTCAE Grade 1 or Grade 0 lymphocyte count.

According to the CTCAE version 4.03 [8], lymphopenia grades are defined as follows:

- Grade 1: < lower limit of normal (LLN) to 800/mm^3 or < LLN to 0.8 × 10^9/L
- Grade 2: < 800–500/mm^3 or < 0.8–0.5 × 10^9/L
- Grade 3: < 500–200/mm^3 or < 0.5–0.2 × 10^9/L
- Grade 4: < 200/mm^3 or < 0.2 × 10^9/L

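### The duration planned for primary endpoint 2 mixes in-trial time, unresolved by the selection rule, with the recovery time seen in the registry; time from trial end should be reported separately

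*SAP*

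**What the plan says.** Protocol 6.1 names the endpoint as "Time to resolution of lymphopenia, among registry participants with persistent lymphopenia". Protocol 6.3 fixes that population at trial exit ("Subjects who complete or drop out of a cladribine clinical trial with a Grade 3 or Grade 4 lymphopenia") and defines the event: "Resolution is the achievement of a CTCAE Grade 1 or Grade 0 lymphocyte count". Under Primary Endpoints in section 9.2.2, the protocol adds that "time to resolution of persistent lymphopenia will be estimated using the life table methodology".

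SAP section 5 gives the timeframe as "Time to resolution of lymphopenia, for participants with ongoing lymphopenia at the end of clinical trial". SAP section 7, Table 1, replaces the life table: "The time to resolution of lymphopenia for participants with ongoing lymphopenia at end of clinical trial will be analyzed using descriptive statistics". The same row glosses time to resolution as the duration of the lymphopenia episode. It says a Kaplan-Meier analysis of that quantity is already in the Integrated Summary of Safety (ISS) and will not be repeated.

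SAP 15.1.4 gives the detail. Subjects qualify if they left the trial without returning to Grade 0/1 after a Grade 3/4 episode. "A grade 3 or 4 lymphopenia episode is defined by a start/end date": it starts at a post-baseline count of Grade 3 or worse and ends at the following Grade 0/1 count. The planned statistic is then: "The duration (in months) of the resolved episodes (out of the unresolved at end of clinical trial period) will be summarized". No other time origin is given.

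**The concern.** Selection is made at trial end, but the clock appears to start earlier. Anyone whose episode resolved before trial end is excluded, so every included subject has a stretch of in-trial time during which resolution could not have been recorded. That stretch depends on when the Grade 3/4 count occurred relative to the end of the subject's last trial, which is a matter of trial design and dosing calendar.

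This matters because it is the endpoint's only planned time measure. The outcome counts, the CRF tick-box summary and the 2-by-2 table are not durations. A reader who wants to know how long a patient leaving the trial with lymphopenia took to recover could not get it from this summary. A reader who took it as the usual length of a Grade 3/4 episode would be looking at episodes selected for having lasted until trial end.

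The problem is separate from the restriction to resolved episodes. Adding the unresolved subjects as censored observations would leave the start date where it is.

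**Working it through.** **1. Which clock the text implies.** An episode that is unresolved at trial end must have started before it. The only start date in SAP 15.1.4 is the first post-baseline Grade 3/4 count, and Table 1 equates time to resolution with episode duration. The natural reading is therefore end date minus in-trial start date. The SAP does not write that formula. SAP 9.7 also defines baseline generally as registry baseline, which cannot be what post-baseline means here. The ALC Study Baseline defined in 15.1.4 itself does fit.

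**2. Decomposition.** For each included subject:

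duration = (trial end − episode start) + (resolution − trial end) = age at trial end + time after trial end.

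The first term is unresolved by selection. Only the second is recovery seen in the registry.

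**3. Illustrative size.** The documents state no duration, so there is no figure of the plan's to reproduce. All inputs here are assumptions: onset uniform over a trial of T months, true durations with mean m, and registry follow-up of F months. For exponential durations the two terms are independent, and among resolved episodes:

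- mean age at trial end = m − T/(e^(T/m) − 1)
- mean time after trial end = m − F/(e^(F/m) − 1)

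The choice F = 96 − T corresponds to the protocol's limit of 8 years from first trial enrolment.

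| m | T | F | Age at trial end | Time after trial end | SAP mean | Share before trial end |
|---|---|---|---|---|---|---|
| 12 | 24 | 72 | 12 − 24/6.389 = 8.2 | 12 − 72/402.4 = 11.8 | 20.1 | 41% |
| 24 | 12 | 84 | 24 − 12/0.6487 = 5.5 | 24 − 84/32.12 = 21.4 | 26.9 | 20% |
| 24 | 12 | 12 | 24 − 12/0.6487 = 5.5 | 24 − 12/0.6487 = 5.5 | 11.0 | 50% |

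In the first row, starting the clock at trial end and including every open episode gives a mean of 12.0 months (median 8.3), against a SAP mean of 20.1 (median 17.6).

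**4. Range.** I varied the distribution (exponential, lognormal with sigma 1, Weibull with shape 1.5), m (6, 12, 24), T (12, 24, 48) and F (12, 48, 96 − T). Because 96 − 48 = 48 duplicates one choice of F, this gives 9 × (3 + 3 + 2) = 72 distinct scenarios.

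- The share of the SAP mean lying before trial end runs from 20% to 76%. It is 20% to 50% when follow-up reaches the 8-year limit.
- The 76% case is Weibull with m = 24, T = 48, F = 12: 17.96 of 23.70 months.
- With follow-up to the 8-year limit, the SAP mean exceeds the mean of all Grade 3/4 episodes in 26 of 27 scenarios, by a factor of up to about 2.3.
- Over all 72, it falls below the all-episode mean in 18, mostly with long episodes and short follow-up. The third table row is one: 11.0 against 24.0 months.

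**5. Effect of the resolved-only step.** Take T = 22 months (96 weeks) and exponential durations, and count all open episodes, resolved or not. Mean total length is then 2m − T/(e^(T/m) − 1):

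- m = 3: 6.0 months
- m = 6: 11.4 months
- m = 12: 19.8 months

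These are roughly 1.7 to 2 times the true mean. They are not the SAP statistic, which drops unresolved episodes and is therefore lower.

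**The case against.** The strongest reply is that no passage sets the clock at trial end. Protocol 6.3 says who is in the population, not when time starts. Protocol 9.2.2 starts its primary analysis period at the first dose of trial medication, and SAP 9.2 keeps one lymphocyte period that starts there too. On this view an in-trial start is a legitimate choice. This stands to the extent that a reader might infer that the SAP contradicts a stated time origin, and the documents do not support that.

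A second tempting inference is that the endpoint is length-biased. For the endpoint as defined, selecting episodes open at trial end is the population itself. Length bias arises only if the figure is read as the duration of Grade 3/4 episodes in general. The SAP does not claim that, and it refers the general question to the ISS, which cannot be seen here.

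Third, onset is unlikely to be uniform. Protocol section 3 describes nadirs at Weeks 16 and 55 after scheduled courses, so the sizes above could move either way. This stands, and they are offered only as a range.

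Fourth, time from trial end also depends on an administrative date, except under an exponential distribution. That is true, and it is why episode age at trial end should be shown beside it.

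Finally, the analysis is descriptive, with no inference planned, and the other resolution outputs are unaffected. That limits the consequence. It does not make a sum of two different quantities interpretable.

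**Conclusion.** The point holds in this form: as naturally read, the only time-to-resolution figure for primary endpoint 2 adds in-trial time, unresolved by selection, to post-trial recovery time, and neither SAP 15.1.4 nor Table 1 says so. It shows neither recovery after leaving the trial nor typical episode duration.

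A reader might go further and infer that the SAP overstates the duration of lymphopenia. The documents do not support that. Summarising resolved episodes only works in the opposite direction, and the net result depends on episode lengths and follow-up that are not given. The 20% to 76% share rests on the assumed distributions, uniform onset and the trial and follow-up lengths listed above. The presence of the in-trial component rests only on reading duration as the episode's end minus its start.

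The change is worth making before the analysis is run: it loses no planned output and lets the registry report what it was placed to observe.

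**What to change.** In SAP 15.1.4:

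- State the time origin explicitly.
- For subjects unresolved at trial end, report time from end of clinical trial (Registry Day 1) to the first Grade 0/1 ALC.
- Give episode age at trial end as a separate descriptive line.
- If total episode duration is also shown, either label it as conditional on being open at trial end or estimate it with delayed entry (left truncation) at trial end.

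How subjects who never resolve are handled is a separate choice that this change does not settle.

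The cost is a short SAP edit and a changed start date in the program. The dates are already held and no new data are needed.

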## 8.4 Follow-Up Interviews

For MS subjects, the information to be ascertained in the follow-up interviews fall into five main categories:

- Updates in contact information
- Occurrence of SAEs (including time of event and outcome)
- Occurrence of AEs in the ‘Blood and Lymphatic System Disorders’ and ‘Neoplasms Benign, Malignant, and Unspecified’ SOCs (including time of event and outcome)
- Capture of any lymphocyte count assessments performed since last visit
- Prescription of immunosuppressant medications including type and start date

It is expected that subjects in PREMIERE will attend their routine MS care visits. The PRP is expected to request blood count and differential if lymphopenia has not resolved (i.e., lymphocyte count is equal or greater than  $0.8 \times 10^9/L$ ). All lymphocyte count results will be captured by the PRP regardless of monitoring frequency. Participating PRP will be instructed to have blood count and differential performed at least yearly until resolution of lymphopenia (i.e., a Grade 1 or Grade 0 lymphopenia), or end of the study period.

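### The date lymphopenia resolves is known only to lie between two blood counts, yet the SAP treats it as exact, and the direction of the net error in the planned summary is not established

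*SAP*

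**What the plan says.** Protocol 6.1 and SAP section 5 make time to resolution, among participants with persistent lymphopenia, a primary endpoint. SAP section 7 (Table 1) drops the protocol's life table: "The time to resolution of lymphopenia for participants with ongoing lymphopenia at end of clinical trial will be analyzed using descriptive statistics".

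The rule is in SAP 15.1.4, in the part based on observed ALC values: "A grade 3 or 4 lymphopenia episode is defined by a start/end date". The start is an ALC of at least "grade 3, post baseline", and the end is given as "End = following normal (grade 0) or grade 1". The output for subjects who left the trial unresolved is: "The duration (in months) of the resolved episodes (out of the unresolved at end of clinical trial period) will be summarized".

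On how often counts are taken, Protocol 8.4 says: "Participating PRP will be instructed to have blood count and differential performed at least yearly until resolution of lymphopenia". It adds: "All lymphocyte count results will be captured by the PRP regardless of monitoring frequency". Protocol 8.2 sets interviews every 3 months for two years and yearly afterwards, but attaches no required blood test to them. For the interval between trial end and registry enrolment, Protocol 8.3.1.1 allows counts to be held by category only when the medical record is not accessible.

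For this endpoint, neither SAP section 7 nor 15.1.4 uses the date of the last unresolved count, reports the gap between counts, or applies an interval-censored method.

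**The concern.** The end date is a detection date. A subject whose last count was Grade 2 or worse, and whose next was Grade 0/1, recovered somewhere between the two. Using the later date as the event time adds the wait for the next test to the recovery time. The figure reported for a primary endpoint then depends partly on how often blood was drawn, and the planned outputs do not show by how much.

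No other output fills the gap. The tick-box analysis gives resolved or unresolved, not a duration. The listing of all ALC values covers only subjects unresolved by ALC grade whose tick box says resolved. The windows in SAP Tables 7 and 8 serve the over-time ALC summaries, not the resolution analysis.

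**Working it through.** **Plan's own figure.** There is none to reproduce. Protocol 9.1 does not size the cohort by estimation, and the documents give no expected duration.

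**Inputs from the documents.** Minimum testing is at least yearly (Protocol 8.4). A 3-month gap is the favourable case if a count accompanies each interview in the first two years (Protocol 8.2). In-trial ALC targets are 2 to 12 weeks apart through Week 105 (SAP Table 7). The conversion is 12 months = 365.25 days (SAP 9.11), so one month is 30.44 days.

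**Step 1: delay in the end date.** If resolution is uniform within a gap *g*, the mean delay is *g*/2.
- Yearly counts: 12/2 = 6.0 months.
- 3-monthly counts: 3/2 = 1.5 months.

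If resolution is instead exponential with rate λ and tests fall at multiples of *g* from trial end, the mean delay is *g*/(1 − e^(−λ*g*)) − 1/λ. For *g* = 12 and an assumed median of 12 months, λ = ln 2/12 and the delay is 12/0.5 − 17.31 = 6.69 months. Over assumed medians from 48 down to 3 months, the delay is 6.2 to 8.5 months with yearly counts and 1.5 to 1.7 months with 3-monthly counts.

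**Step 2: delay in the start date.** The start is the first observed count of Grade 3 or worse, so it is also late, and this shortens the duration. Taking half the target spacing:
- 2-week spacing: 7/30.44 = 0.2 months.
- 12-week spacing: 42/30.44 = 1.4 months.

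**Step 3: net error in a resolved duration** (uniform case, end delay minus start delay).
- Yearly counts: 6.0 − 1.4 = +4.6 to 6.0 − 0.2 = +5.8 months.
- 3-monthly counts: 1.5 − 1.4 = +0.1 to 1.5 − 0.2 = +1.3 months.

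This was simulated with 400,000 episodes per scenario, exponential resolution after trial end and start gaps of 4 or 12 weeks. The reported duration was shorter than the true one in 4% to 12% of episodes with yearly counts and in 15% to 46% with 3-monthly counts.

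**Step 4: effect of summarising resolved episodes only.** The same simulation assumes 48 months of follow-up after trial end and 1 to 12 months from observed start to trial end. With a 12-week start gap:

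| Registry counts | Assumed median from trial end (months) | Resolved | Mean reported duration, resolved only (months) | True mean, all (months) |
|---|---|---|---|---|
| Yearly | 6 | 99% | 20.8 | 16.5 |
| Yearly | 12 | 91% | 25.7 | 25.2 |
| Yearly | 24 | 70% | 29.2 | 42.4 |
| 3-monthly | 6 | 99.5% | 16.4 | 16.5 |
| 3-monthly | 12 | 93% | 21.9 | 25.2 |
| 3-monthly | 24 | 74% | 26.2 | 42.5 |

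The planned summary can be too long, about right or much too short, depending on the testing gap and the share resolved. Neither is given in the documents.

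**The case against.** Yearly testing is a floor. Protocol 8.4 expects a count to be requested while lymphopenia persists and captures every result, count results are collected at each contact, and SAP Table 8 uses roughly 12-week windows up to Week 96. Denser data may well exist, and at 3-monthly counts the net error in a duration is close to zero to one month. This stands: the size cannot be fixed from the documents. It also means that the gap is worth reporting.

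Protocol 6.3 defines resolution as reaching a Grade 0/1 count, the SAP heading says observed values are used, and the analysis is descriptive with no inference planned. Dating resolution at the observed count therefore follows the definition and is disclosed. This is fair, but the definition says what resolution is. It does not make the date exact, and a reader of the duration table could not see the testing interval behind it.

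SAP section 7 says a Kaplan-Meier analysis of episode duration is already in the Integrated Summary of Safety. The long-term data cut-off given there is 15 May 2017, before the last visit on 25 October 2018, and the documents do not say how detection delay was handled.

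Three stronger readings are tempting and are not supported:
- **Each reported duration is an upper bound.** This is true of the resolution date, or of time from a fixed origin. It is not true of the SAP duration, whose start is also detected late.
- **The summary is about half a testing gap too long.** Leaving out unresolved episodes pulls the other way.
- **Sparsely tested sites will be shown as slower to recover.** SAP 15.1.4 specifies no duration by site or by testing density.

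**Conclusion.** The resolution date is interval-censored and the SAP analyses it as exact. On average the date is late by half the testing gap, which is 1.5 months for 3-monthly counts and 6 months for yearly counts if resolution is uniform within the gap. After allowing for the late start, the net error in a resolved duration runs from near zero at 3-monthly testing to roughly 5 months at yearly testing. The direction of error in the summary as a whole is not established, because unresolved episodes are left out and the actual gaps and share resolved are unknown.

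The half-gap figures rest on uniform resolution within the gap. The start delay rests on SAP Table 7 target spacing as a proxy for in-trial testing. The recovery medians, exponential shape and follow-up length in the simulation are assumptions, not document figures. The point is a cheap improvement to a primary-endpoint summary. It does not show that the planned figure is wrong in a known direction.

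**What to change.** For each subject with unresolved lymphopenia at the end of the clinical trial:

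1. Carry two dates: the last ALC of Grade 2 to 4 before resolution, and the first Grade 0/1 ALC.
2. Measure time to resolution from the end of the clinical trial (SAP 9.8). This is a fixed date and the point at which these subjects are selected, so it avoids both the late start and the selection problem of counting from an in-trial onset.
3. Estimate the distribution with an interval-censored (Turnbull) method, for example SAS PROC ICLIFETEST. Keep subjects who never resolve, right-censored at their last ALC.

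At minimum, or if numbers are small, tabulate the earliest and latest possible time to resolution from trial end and the length of the testing gap. Place these beside the planned summary, together with the number unresolved.

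The cost is a short SAP text change and a little programming. The ALC values and dates are already collected. The estimate will be less sharp, because it shows the uncertainty that the testing schedule leaves.
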